7.3.3 Visits during active treatment phase

7.3.3.1For all patients in AG019 cohorts and Combination Cohorts

7.3.3.1.1Day 4 follow-up visit

Following observations and procedures will be completed:

- Register visit in IRT
- Physical Exam
- Vital Signs
- Urine pregnancy test (in women of childbearing potential)
- Blood sampling for local lab (hematology, full chemistry, INR)
- Record concomitant medications
- Record adverse events
- Study drug accountability
- ePRO review including insulin use and hypoglycemic events
- CGM readings/download
- Evaluation of drug infusion withholding criteria (only for Combination Cohorts)
- Teplizumab/placebo (randomized treatment should be respected) infusion

7.3.3.1.2Day 7 follow-up visit

Confidentiality Statement

Following observations and procedures will be completed:

- Register visit in IRT
- Physical Exam
- Vital Signs
- Urine pregnancy test (in women of childbearing potential)
- Blood sampling for local lab (hematology, full chemistry, INR)
- Record concomitant medications
- Record adverse events
- ePRO review including insulin use and hypoglycemic events
- CGM readings/download
- Evaluation of drug infusion withholding criteria (only for Combination Cohorts)
- Teplizumab/placebo (randomized treatment should be respected) infusion
- Study drug accountability

7.3.3.1.3Day 12 follow-up visit

Following observations and procedures will be completed:

- Register visit in IRT
- Physical Exam
- Vital Signs
- Urine pregnancy test (in women of childbearing potential)
- Blood sampling for local lab (hematology, full chemistry, INR)
- Record concomitant medications
- Record adverse events
- Infectious disease monitoring (PCR)
- Blood sample for central lab PK
- Blood sample for mechanistic assessments (only for repeat dose patients in AG019 Cohorts 2 and 4 and for patients in the combination cohorts)
- ePRO review including insulin use and hypoglycemic events
- CGM readings/download
- Evaluation of drug infusion withholding criteria (only for Combination Cohorts)
- Teplizumab/placebo (randomized treatment should be respected) infusion including blood sample for safety labs and evaluation of drug infusion withholding criteria (only for Combination Cohorts)
- Study drug accountability

7.3.3.1.4Day 28 follow-up visit

Following observations and procedures will be completed:

Confidentiality Statement

- Register visit in IRT
- Physical Exam
- Vital Signs
- Urine pregnancy test (in women of childbearing potential)
- Blood sampling for local lab (hematology, chemistry)
- Record concomitant medications
- Record adverse events
- Infectious disease monitoring (PCR)
- ePRO review including insulin use and hypoglycemic events
- CGM readings/download
- AG019/placebo dispensing (for combination cohorts, randomized treatment should be respected)
- AG019 drug accountability

7.3.3.1.5Day 56 follow-up visit (End of Treatment)

Following observations and procedures will be completed:

- Physical Exam
- Vital Signs
- 12-lead ECG
- Urine pregnancy test (in women of childbearing potential)
- Blood sampling for local lab (hematology, chemistry)
- Blood sampling for mechanistic assessments (only for repeat dose patients in AG019 Cohorts
 2 and 4 and for patients in the combination cohorts)
- Blood sampling for central lab (HbA1c)
- Blood sample for central lab PK
- Feces collection for central lab PK (only for repeat dose patients in AG019 Cohorts 2 and 4 and for patients in the combination cohorts)
- Record concomitant medications
- Record adverse events
- Infectious disease monitoring (PCR)
- AG019 drug accountability
- ePRO review including insulin use and hypoglycemic events
- CGM readings/download

Confidentiality Statement

7.3.3.2Additional visits for patients in Combination Cohorts

For patients in the Combination cohorts, additional follow-up visits for teplizumab infusions will take place on Day 2, Day 3, Day 5, Day 6, Day 8, Day 9, Day 10 and Day 11. During each of these visits, following observations and procedures will be completed:

- Register visit in IRT
- Record concomitant medications
- Record adverse events
- Teplizumab infusion including blood sample for safety labs and evaluation of teplizumab infusion withholding criteria

7.3.3.3Additional feces sampling (at home) on Days 58, 60, 62 and 64 (only for repeat dose patients in AG019 Cohorts 2 and 4 and for patients in the combination cohorts)

After the Day 56 follow-up visit, patients in AG019 Cohorts 2 and 4 and in the combination cohorts will be asked to collect additional feces samples every other day until Day 64. The samples will be collected and kept in the patient's freezer, and will be handed over to the site personnel during the next follow-up visit. Sites can arrange for a courier to pick up the collected samples from the patient's home after Day 64, if the patient does not want to store the feces samples in his/her freezer until the next site visit (Day 90).

Details on collection, labelling and storage of the samples will be explained verbally and in writing to the patients.

A 2-day visit window is allowed for the Day 56 visit. The first feces sample will be collected in the hospital on the Day 56 follow-up visit, regardless on which day this visit takes place. If it is not possible to collect a feces sample at the site, the sample collection equipment will be given to the patient and a sample will be collected at home, ideally on the same day. Subsequent samples will be collected every 2 days following this visit, as described in the below table.

EOT visit date	First sample	Second sample	Third sample	Fourth sample	Fifth sample
D54	D54	D56	D58	D60	D62
D55	D55	D57	D59	D61	D63
D56	D56	D58	D60	D62	D64
D57	D57	D59	D61	D63	D65
D58	D58	D60	D62	D64	D66

Confidentiality Statement

7.3.4Visits after the active treatment phase

7.3.4.1Day 90 follow-up visit

Following observations and procedures will be completed:

- Physical Exam
- Vital Signs
- Urine pregnancy test (in women of childbearing potential)
- Blood sampling for local lab (hematology, chemistry)
- Infectious disease monitoring (PCR)
- Blood sampling for mechanistic assessments (only for repeat dose patients in AG019 Cohorts
 2 and 4 and for patients in the combination cohorts)
- Blood sampling for central lab (HbA1c)
- Blood sample for central lab PK
- Mixed Meal Tolerance Test (MMTT)
- Record concomitant medications
- Record adverse events
- ePRO review including insulin use and hypoglycemic events
- CGM readings/download

7.3.4.2Day 180 follow-up visit

Following observations and procedures will be completed:

- Physical Exam
- Vital Signs
- Urine pregnancy test (in women of childbearing potential)
- Blood sampling for local lab (hematology, chemistry)
- Blood sampling for mechanistic assessments (only for repeat dose patients in AG019 Cohorts
 2 and 4 and for patients in the combination cohorts)
- Blood sampling for central lab (HbA1c)
- Mixed Meal Tolerance Test (MMTT)
- Record concomitant medications
- Record adverse events
- ePRO review including insulin use and hypoglycemic events
- CGM readings/download
- 12-lead ECG (only if there is suspicion of cardiac problems)

7.3.4.3Day 270 follow-up visit

Following observations and procedures will be completed:

- Physical Exam
- Vital Signs
- Urine pregnancy test (in women of childbearing potential)

Confidentiality Statement

- Blood sampling for local lab (hematology, chemistry)
- Blood sampling for mechanistic assessments (only for repeat dose patients in AG019 Cohorts
 2 and 4 and for patients in the combination cohorts)
- Blood sampling for central lab (HbA1c)
- Record concomitant medications
- Record adverse events
- ePRO review including insulin use and hypoglycemic events
- CGM readings/download

7.3.4.4Day 360 follow-up visit (End of Study)

Following observations and procedures will be completed:

- Physical Exam
- Vital Signs
- Urine pregnancy test (in women of childbearing potential)
- Blood sampling for local lab (hematology, chemistry)
- Infectious disease monitoring (PCR)
- Blood sampling for mechanistic assessments (only for repeat dose patients in AG019 Cohorts
 2 and 4 and for patients in the combination cohorts)
- Blood sampling for central lab (HbA1c)
- Mixed Meal Tolerance Test (MMTT)
- Record concomitant medications
- Record adverse events
- ePRO review including insulin use and hypoglycemic events
- CGM readings/download
- 12-lead ECG

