5.4. Labelling, Packaging and Storage

XXX

5.5.Investigational Medicinal Product Administration

XXX

Detailed instructions for dose preparation and dispensing to patients will be provided to the clinical site by the Sponsor or its designee.

Confidentiality Statement

Total bilirubin, AST, ALT, LDH, Complete Blood Count (CBC), and INR will be evaluated to verify the need to withhold teplizumab (or placebo) infusion prior to each (potential) teplizumab administration, as described in Appendix A. The drug infusion withholding criteria presented in Section 11.4.3.5 should be evaluated.

5.6.Placebo/Comparator

XXX

AG019 placebo and teplizumab placebo will be packaged identically to their active counterparts and will be matched for size, color and taste (as applicable), to prevent possible breaches in the blinding.

Administration of placebo will be identical to administration of its respective active treatment.

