 the baseline visit. The CGM device will be placed, so the patient will know how to do this at
 home. The placement of the CGM, as well as the first CGM reading, will be done prior to
 administration of the first dose of study drug(s). The Sponsor will supply the CGM devices.
- **Tuberculosis test:** As part of the eligibility verification, all patients will undergo a test to determine whether the patient shows signs of active or latent tuberculosis. The decision on the type of test to be used is left to the discretion of the investigator, and could include e.g. TST, TSPOT, QuantiFeron or other appropriate tests.
- Concomitant medications: At every visit, the investigator will obtain information about concomitant medications the patient is taking (including dose, frequency, route of administration, start and stop dates)

6.2.Safety Assessments

Safety will be assessed by collecting and recording Adverse Events (AEs) and laboratory assessments and the presence of *L. lactis* sAGX0407 in whole blood.

The study will utilize local laboratories for safety assessments. The clinical laboratory will indicate laboratory values out of normal ranges. The Investigator must assess all abnormal clinical laboratory results for clinical significance in a timely fashion. A notation of 'clinically significant' (CS) or 'non-clinically significant' (NCS) with initials and date will be documented on the respective laboratory report next to any abnormal value. An abnormal clinical laboratory value will be considered and documented as an AE, if in the opinion of the Investigator, it is clinically significant. The Investigator will follow proper adverse event reporting procedures.

For details on the data to be collected for adverse events, please refer to Section 8.

XXX

6.3.Laboratory Assessments

6.3.1General considerations

Throughout the study, blood samples will be collected at regular intervals, as described in the Visit schedule

XXX

Confidentiality Statement

XXX

6.3.2Local lab assessments

Parameters to be analysed will include:

- Hematology: complete blood count: Red Blood Cell (RBC) count, haemoglobin, haematocrit, mean corpuscular volume (MCV), mean corpuscular haemoglobin (MCH), mean corpuscular haemoglobin concentration (MCHC), RBC distribution width (RDW), white blood cell (WBC) count, differential count, platelet count
- Serum Chemistry: blood glucose, sodium, potassium, chloride, calcium, CO₂/bicarbonate

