10.7. Safety Analysis

Safety will be assessed based on TEAEs, physical examination findings, vital sign measurements and clinical laboratory tests.

Adverse events will be coded to a Medical Dictionary for Regulatory Activities (MedDRA) preferred term and system organ classification. The occurrence of treatment emergent AEs will be summarized by treatment frequency received using preferred terms, system organ classifications and severity. If a patient experiences multiple events that map to a single preferred term, the greatest severity and/or strongest investigator assessment of relation to study drug will be assigned to the preferred term for the appropriate summaries. Separate summaries of treatment emergent SAEs and treatment emergent AEs that are related to either IMP will be generated. Summaries may be repeated according to study phase. All AEs will be listed for individual patients showing both verbatim and preferred terms.

Descriptive summaries of vital signs and quantitative clinical laboratory changes will be presented by treatment received and study visit. The number and percentage of patients experiencing laboratory abnormalities and clinically relevant laboratory abnormalities will be summarized by treatment received. Cross tabulations of baseline abnormality vs. worst post treatment abnormality for selected laboratory assessments will presented by treatment received.

Abnormal physical examination findings will be presented by treatment received. The number and percentage of patients experiencing each abnormal physical examination finding will be included.

Prior and concomitant medications will be coded using the World Health Organization (WHO) dictionary. These data will be listed.

The number and percentage of patients with presence of sAGX0407 bacteria will be summarized by treatment group.

10.8.Interim Analysis

Interim analyses will be performed according to the below schedule:

After the last Day 180 follow-up visit of the last patient enrolled into the Phase 1b portion of
the study, a preliminary analysis of the data collected up to 6 months will be performed for
these patients.

Confidentiality Statement

- Once all patients enrolled in Combination Cohort 1, as well as the 2 patients enrolled into the
 open label portion of Combination Cohort 2, have completed the Day 180 follow-up visit,
 unblinding will be done and an interim analysis will be performed.

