4 OVERALL STUDY DESIGN

4.1 Overview of Study Design

This Phase 1b/2a, multi-center study is conducted in patients with clinical recent-onset Type 1 Diabetes Mellitus (T1D).

AG019 is the genetically modified *L. lactis*, strain sAGX0407, containing the gene sequences coding for hPINS and hIL-10, and comprising an environmental containment system, formulated for oral administration as gastro-resistant hard capsules.

In addition to the scheduled 19 clinic visits, all patients were asked to keep a diary for collection of information relating to the study drug intake, concomitant medication intake, occurrence of AEs including hypoglycemic and hyperglycemic events, and insulin use. A detailed schedule on the measurements for each visit can be found in the Appendix A to the CSP. Information on when the measurements were planned to be collected can also be found under each subsection in this SAP.

Eight (8) single dose patients and a maximum of 48 repeat dose patients were allowed to be enrolled in clinical sites in the US and Belgium. AG019 was administered twice daily for 8 weeks at either a low dose (2 capsules/d) or at a high dose (6 capsules/d). This study consists of 2 phases and 6 cohorts. All repeat dose patients in all cohorts described below will be followed up for a total of 12 months (8 weeks of treatment plus 10 months of post-treatment follow-up).

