If the start date of an AE is missing, it will be assumed that the AE started after the first administration of IMP. If the start date of an AE is partially missing, and it has started the same year and/or month as the IMP it will be assumed that the AE started after the first administration of IMP. If an AE occurred on the same day as dosing but the onset time is missing the AE will be assumed to be a TEAE.

The infusion of teplizumab was considered withheld if the answer to the CRF question 'Was the Teplizumab infusion given?' was 'No, infusion not started' and/or if the answer on the AE page on 'Action Taken With Study Treatment Teplizumab' was 'Drug interrupted' or 'Drug withdrawn'.

Study treatment of AG019 was considered discontinued if the answer to the CRF question "Action Taken with Study Treatment AG019" was "Drug interrupted" or "Drug withdrawn".

A summary table per cohort will present number of TEAEs, number of unique TEAEs (counted once within each subject at the preferred term level) and number of subjects with at least one event for TEAEs, SAEs, related TEAEs, TEAEs leading to discontinuation of IMP/withdrawal and more.

Tables with

- All AEs by System Organ Class (SOC) and PT,
- All TEAEs by SOC and PT, in total and for the AG019 treatment period only,
- All TEAEs by SOC and PT according to severity, in total and for the AG019 treatment period only,
- All TEAEs by SOC and PT according to relatedness, in total and for the AG019 treatment period only,
- All serious TEAEs by SOC and PT,

will be given. If there are no events an empty table will be produced.

All AEs will be listed. In addition all TEAEs leading to AG019 treatment discontinuation and study infusion withholding will be listed.

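### Eight extra safety-lab and AE visits in the combination cohorts can raise their any-abnormality, worst-value and lab-derived TEAE rates relative to AG019 alone; add common-visit versions of these summaries

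*Protocol*

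**What the plan says.** - **Extra visits.** Protocol 7.3.3.2 states for combination patients that "additional follow-up visits for teplizumab infusions will take place on Day 2, Day 3, Day 5, Day 6, Day 8"; the full list of days is "Day 2, Day 3, Day 5, Day 6, Day 8, Day 9, Day 10 and Day 11". Each visit records adverse events and includes "Teplizumab infusion including blood sample for safety labs and evaluation of teplizumab infusion withholding criteria".
- **Tests drawn.** Protocol 5.5 lists them: "Total bilirubin, AST, ALT, LDH, Complete Blood Count (CBC), and INR will be evaluated to verify the need to withhold teplizumab (or placebo) infusion".
- **Common visits.** Protocol 7.3.3.1 and 7.3.4 give all repeat-dose patients, in both AG019 and combination cohorts, AE recording and local labs on Days 4, 7, 12, 28, 56, 90, 180, 270 and 360.
- **From lab value to AE.** Protocol 6.2: "An abnormal clinical laboratory value will be considered and documented as an AE, if in the opinion of the Investigator, it is clinically significant". The primary endpoint is TEAE incidence up to the 6-month visit.
- **Lab summaries in the protocol.** Section 10.7: "The number and percentage of patients experiencing laboratory abnormalities and clinically relevant laboratory abnormalities will be summarized by treatment received". It also plans a cross-tabulation of baseline against worst post-treatment abnormality.
- **Lab summaries in the SAP.** Sections 6.3.9 and 7.1 list by-visit summaries and by-visit shift tables. They list no any-abnormality or worst-value table, although SAP 6.1 reports no change to the planned analyses.
- **TEAE tables.** SAP 6.3.8 plans "All TEAEs by SOC and PT, in total and for the AG019 treatment period only". The overview table counts events and subjects with at least one event, with no allowance for the number of visits.
- **Visit count.** SAP 4.1: "In addition to the scheduled 19 clinic visits, all patients were asked to keep a diary".

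**The concern.** A summary that asks whether a patient was ever abnormal, or how bad the worst value was, depends on how often the patient was sampled. Here sampling differs sharply between AG019 alone and the combination, and only during the infusion period. Clinically significant values become AEs, so the same imbalance can reach the primary endpoint through lab-derived TEAEs.

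The contrast matters although no test is planned. The randomised comparison is double active against double placebo, so it cannot show what teplizumab adds to AG019. AG019 Cohorts 2 and 4 against the combination cohorts share the planned 6 capsules and the age groups, and this is the only contrast in the trial that bears on that question. Part of a higher abnormality rate in the combination could come from daily blood draws.

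**Working it through.** **1. Reproduce the SAP's visit count.** Visits common to all repeat-dose patients (protocol 7.3) are screening and Days 1, 4, 7, 12, 28, 56, 90, 180, 270 and 360, which makes 11. Combination-only visits are Days 2, 3, 5, 6, 8, 9, 10 and 11, which makes 8. 11 + 8 = 19, the SAP 4.1 figure. It is therefore the combination schedule. The SAP's visit list for vital signs and physical examination in repeat-dose patients (1, 2, 5, 8, 13-19) has 11 entries, which matches the common schedule. Single-dose patients have 3 visits (protocol 7.2).

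**2. Post-baseline visits with AE recording and safety labs.**

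| Window | AG019 alone | Combination |
|---|---|---|
| Day 2 to Day 12 | 3 | 11 |
| Day 2 to Day 56 | 5 | 13 |
| Day 2 to Day 180 | 7 | 15 |

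The SAP's existing split, total against AG019 treatment period, does not help: 13/5 = 2.6 is more unequal than 15/7 = 2.1.

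**3. Effect on having at least one abnormal draw.** Take the same true per-draw rate p in both groups. For k independent draws, P(any) = 1 − (1 − p)^k. For within-patient correlation ρ, use a beta-binomial with s = (1 − ρ)/ρ, a = ps and b = (1 − p)s, so that P(any) = 1 − B(a, b + k)/B(a, b), where B is the beta function. The documents give neither p nor ρ; both are assumptions. Results to Day 180 (k = 7 against 15):

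| p | ρ | AG019 alone | Combination | Ratio |
|---|---|---|---|---|
| 1% | 0 | 6.8% | 14.0% | 2.06 |
| 2.5% | 0 | 16.2% | 31.6% | 1.95 |
| 5% | 0 | 30.2% | 53.7% | 1.78 |
| 2.5% | 0.3 | 8.8% | 12.1% | 1.38 |
| 2.5% | 0.6 | 5.4% | 6.5% | 1.22 |
| 2.5% | 0.9 | 3.1% | 3.3% | 1.07 |

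Over p from 0.5% to 10% and ρ from 0 to 0.9, the ratio runs from 1.06 to 2.10. It never falls below 1.

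**4. Dependence on duration.** Let an abnormality start with equal chance on any of Days 2-12 (11 possible start days). Sampling on Days 4, 7 and 12 catches a 1-day abnormality for 3/11 = 27% of start days and a 3-day one for 9/11 = 82%. The longest unsampled run is Days 8-11, so anything lasting 5 days or more is always caught. Daily sampling catches all of them.

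**5. A caveat on the counts.** Appendix A is not in the text available, so the counts rest on protocol 7.3. They assume that the liver tests fall under the chemistry drawn after Day 12. Section 7.3 names INR only up to Day 12. If that is complete, the INR counts are 11 against 3, and its ratio can be larger: at p = 2.5% and ρ = 0, 1 − 0.975^11 = 24.3% against 1 − 0.975^3 = 7.3%.

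**6. After restriction to common visits.** Visits 5, 8 and 13-17 give 7 draws to Day 180 in every repeat-dose group, so the ratio of draws is 1.0.

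**The case against.** The strongest reply is that this reaches less of the plan than it seems to.

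- **Diary.** All repeat-dose and combination patients keep an electronic diary of adverse events from consent to study end (protocol 6.4.1), and protocol 8.4 names it as an AE source. A reader might infer that TEAE rates as a whole are inflated in the combination; the documents do not support that. The clear route is lab-derived events, limited to CBC, bilirubin, AST, ALT, LDH and INR. More frequent questioning may also elicit events, but that cannot be shown from the text.
- **SAP outputs.** By-visit summaries and shift tables are not distorted at matched visits. This stands. The exposed lab tables are those of protocol 10.7, which the SAP neither lists nor withdraws.
- **Size.** A reader might take the independent-draw figures as the expected gap. Most of the extra draws are a day apart in the same patient, so independence is the extreme case. With 4 to 6 repeat-dose patients per AG019 cohort, one patient is already 17 to 25 percentage points.
- **No comparison planned.** The study is descriptive, the AE overviews for AG019 repeat-dose and combination patients are separate tables, and the contrast is not randomised. Equal visit counts would not make it an estimate of teplizumab's effect. This too stands. However, SAP 6.3.2 presents results per cohort and treatment group, and readers will set them side by side.
- **Comparing only after Day 12.** This may look like the natural remedy because the schedules then match. It would remove the whole infusion period from the safety comparison and trade excess detection for a bias toward no difference.

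The listings carry relative day, so Day 1-12 events can be found by hand. That is no substitute for a table.

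**Conclusion.** The concern holds in a limited form. Any-abnormality and worst-value lab summaries by treatment received, and TEAEs derived from the six named tests or panels, are not comparable between the combination and AG019-alone cohorts when all visits are used. The distortion is upward for the combination. For tests drawn at every common visit, its size to Day 180 runs from almost none to about double, depending on the assumed per-draw rate and correlation; for INR it could be larger if no later draws are scheduled. Real drug effects and extra detection coincide in the infusion period, and the all-visit figures cannot separate them. Placebo patients in the combination cohorts have the same eight visits, so the randomised contrast is unaffected. This is a cheap improvement to the presentation, not a flaw that undermines the trial.

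**What to change.** 1. Where an any-abnormality or worst-value lab summary covers both AG019 and combination cohorts, show a version built from the common post-baseline visits only (Visits 5, 8 and 13-19) beside the all-visit version. This keeps Days 4, 7 and 12, so the infusion period stays visible.
2. Show the infusion-day labs (Visits 3, 4, 6, 7 and 9-12) in a combination-only table, active and placebo.
3. In SAP 6.3.8 and 7.1, add Day 1-12 and Day 13-180 columns to the repeat-dose TEAE tables. Present both periods, and state that lab-derived TEAEs from Days 1-12 are not comparable between AG019-alone and combination cohorts.
4. Reconcile protocol 10.7 with SAP 6.3.9 and 7.1: either list the any-abnormality and worst-value tables in the SAP or record their removal as a change.
5. Correct SAP 4.1 to 19 visits for combination, 11 for AG019 repeat-dose and 3 for single-dose patients.

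The cost is SAP wording, one additional table and a few extra columns. No new data, visits or clinical changes are needed.

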5. STUDY TREATMENT

5.1.Treatments

5.1.1AG019

Single dose patients will be treated with (2 or 6 capsules of) AG019.

All patients in the repeat dose cohorts, and all patients in the combination cohorts who are randomized to study treatment, will be treated for 8 weeks with AG019 with one of the doses listed in Table 2:

Table 2: AG019 dosing regimens for repeat dose patients

Dose	Number of capsules	Total daily dose	Treatment duration
Low dose AG019	2 (1 morning, 1 evening)	XXX	8 weeks
High dose AG019	6 (3 morning, 3 evening)	xxx	8 weeks

The total treatment duration for repeat dose patients is 8 weeks or 56 days. Patients will be required to take AG019 for 56 days, even if the Day 56 follow-up visit is not scheduled on Day 56 (there is a 2-day visit window on the Day 56 follow-up visit).

- If the Day 56 follow-up visit is scheduled on Day 54 or Day 55, patients will take their remaining AG019 home again and will continue to take AG019 until the evening dose on Day 56. The patients will then take their remaining AG019 back to the site on Day 90 for final accountability
- If the Day 56 follow-up visit is scheduled on Day 57 or Day 58, patients should be instructed to take AG019 until the evening dose on Day 56.

The daily dose of AG019 to be used in the Phase 2a portion of the study (combination cohorts) is not yet known and will be determined by the results of the Phase 1b portion of the study (AG019 cohorts). Based upon the data obtained in the nonclinical studies, the Sponsor anticipates that a 6-capsule regimen will be administered in the combination cohorts. Following rules will apply:

If the DSMB concludes that no safety concerns are associated with the high dose of AG019 (6 capsules per day) in the Phase 1b portion of the study (AG019 cohorts), the patients enrolled

Confidentiality Statement

in the Phase 2a portion of the study (combination cohorts) will take the high dose of AG019 for 8 weeks.

If the DSMB concludes that safety concerns are associated with the high dose of AG019 (6 capsules per day) in the Phase 1b portion of the study (AG019 cohorts) and that no safety concerns are associated with the low dose of AG019 (2 capsules per day), the DSMB will recommend lowering the AG019 dose in all ongoing and planned (AG019 and) combination cohorts.

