7.3. Repeat Dose Patients

7.3.1Screening Visit (Day -28 – Day 0)

Following screening observations and procedures will be completed within 28 days prior to randomization:

- Signed and dated ICF
- Assessment against inclusion and exclusion criteria
- Medical history
- Demographic Data
- Physical Exam
- Vital signs
- 12-lead ECG
- Serum pregnancy test (in females of childbearing potential)
- Blood sampling for local lab (hematology, full chemistry, specific screening blood analysis, infectious disease, autoantibodies)
- SARS-Cov2 PCR test (only applicable for patients in the combination cohorts)
- Blood sampling for mechanistic assessments (only for repeat dose patients in AG019 Cohorts
 2 and 4 and for patients in the combination cohorts)
- Blood sampling for central lab (HbA1c)
- Blood sample for central lab PK
- Feces collection for central lab PK¹⁰ (only for repeat dose patients in AG019 Cohorts 2 and 4 and for patients in the combination cohorts)
- Tuberculosis test
- Mixed Meal Tolerance Test (MMTT) for C-peptide and glucose assessments
- Drugs of abuse test
- Record concomitant medications
- Record adverse events
- ePRO preparation / explanation
- Assessment of insulin use and hypoglycemic events
- Register patient in IRT
 - Registration in IRT should be done as soon as eligibility is confirmed and ICF is signed to allow for timely shipment of study drug. Ideally this should be done at least 1 week before the Day 1 visit (start of treatment visit).

7.3.2Baseline Visit (Day 1 – start of active treatment)

Prior to the first administration of IMP, following observations and procedures will be completed:

Confidentiality Statement

This document contains confidential information. It is intended solely for the use of the principal investigator, coinvestigators, staff, appropriate institutional review boards or ethical committees, and other required regulatory bodies.

AG019-T1D-101 CSP Final 9.0 11-Jun-2020

¹⁰ Sites should make every reasonable effort to collect feces during the screening visit. If feces cannot be collected during the screening visit, patients will be asked to collect feces between the Screening visit and the Day 1 visit, according to the instructions provided by the site and the collection materials provided by the central lab.

- SARS-Cov2 PCR test (only applicable for patients in the combination cohorts, to be taken within
 3 days before the first teplizumab/placebo infusion)
- Register visit in IRT
- Physical Exam
- Vital Signs

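### End-of-treatment feces samples are timed from the Day 56 visit rather than the last dose, so post-dose timing varies by 4 days and Day 57 or 58 visits give no dosing-day feces sample

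*Protocol*

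**What the plan says.** **Dosing.** Protocol Section 5.1.1 fixes the last AG019 dose at the evening of Day 56 on either side of the visit window. For a visit on Day 54 or 55, "patients will take their remaining AG019 home again and will continue to take AG019 until the evening dose on Day 56". For a visit on Day 57 or 58, "patients should be instructed to take AG019 until the evening dose on Day 56".

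**Feces sampling.** Section 7.3.3.3 is headed as "feces sampling (at home) on Days 58, 60, 62 and 64", and its opening paragraph ends the series at Day 64. It then says "A 2-day visit window is allowed for the Day 56 visit" and "The first feces sample will be collected in the hospital on the Day 56 follow-up visit, regardless on which day this visit takes place". For the rest, "Subsequent samples will be collected every 2 days following this visit". A table gives the five sample days for each possible visit day. Sampling applies to repeat dose patients in AG019 Cohorts 2 and 4 and to the combination cohorts.

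**Other PK samples.** The only other feces sample in Section 7 is at screening: "If feces cannot be collected during the screening visit, patients will be asked to collect feces between the Screening visit and the Day 1 visit". Blood is sampled more often. The Day 12 visit in Section 7.3.3.1.3 lists "Blood sample for central lab PK", and the Day 56 visit lists it again.

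**Analysis.** Presence of the bacteria in feces is the local-exposure part of a secondary objective (Section 2.2). Section 10.5 evaluates blood PK by treatment group and study visit and gives no timing rule for feces. Section 10.3.2 defers PK detail to the SAP, but SAP Sections 1 and 3.2 leave PK out. Section 6.3.3.1 requires each stool sample to carry its collection date and time.

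**The concern.** The series has two uses: to show local exposure while the patient is taking AG019, and to show clearance after dosing stops. Both depend on time relative to the last dose. Because the clock starts at the visit, the same sample number means different things in different patients. At the early edge of the window, part of the series falls during dosing and follow-up after the last dose is short. At the late edge, the whole series falls after dosing has stopped.

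The groups are small: 4 to 6 repeat dose patients in each of AG019 Cohorts 2 and 4, and 12 patients per combination cohort, placebo included. A few off-day visits can change a descriptive summary of how many patients carry the bacteria on treatment and for how long afterwards.

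**Working it through.** **Inputs.** Last dose: evening of Day 56 (Section 5.1.1). Visit day V: 54 to 58. Sample days: the table in Section 7.3.3.3.

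**Reproducing the table.** Sample day = V + 2(k − 1), for k = 1 to 5. This gives all 25 cells. For V = 54 it gives 54, 56, 58, 60 and 62; for V = 58 it gives 58, 60, 62, 64 and 66.

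**Timing against the last dosing day.** Offset = sample day − 56. A sample counts as a dosing-day sample if its offset is 0 or less.

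| Visit day | Sample days | Offset from Day 56 | On or before Day 56 | After Day 56 |
|---|---|---|---|---|
| 54 | 54, 56, 58, 60, 62 | −2, 0, +2, +4, +6 | 2 | 3 |
| 55 | 55, 57, 59, 61, 63 | −1, +1, +3, +5, +7 | 1 | 4 |
| 56 | 56, 58, 60, 62, 64 | 0, +2, +4, +6, +8 | 1 | 4 |
| 57 | 57, 59, 61, 63, 65 | +1, +3, +5, +7, +9 | 0 | 5 |
| 58 | 58, 60, 62, 64, 66 | +2, +4, +6, +8, +10 | 0 | 5 |

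**Range by sample number, over visit days 54 to 58.**
- Sample 2: 0 to +4.
- Sample 3: +2 to +6.
- Sample 4: +4 to +8.
- Sample 5: +6 to +10.
- Sample 1: −2 to +2 by calendar. Patients seen on Days 54 to 56 are still dosing, so their time off drug is about 0; for Days 57 and 58 it is about 1 and 2 days. The true off-drug range for sample 1 is therefore about 0 to 2 days.

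**Heading against table.** Days 58, 60, 62 and 64 appear as samples 2 to 5 in one row only, the Day 56 visit. The last sample falls anywhere from Day 62 to Day 66.

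**How likely are off-day visits?** Section 7.3.2 recommends a Monday Day 1 for the combination cohorts. Day 7 is then a Sunday, and 56 = 8 × 7, so Day 56 is also a Sunday. The window runs Friday (Day 54), Saturday (55), Sunday (56), Monday (57) and Tuesday (58). The weekday choices are Days 54, 57 and 58. The first leaves three post-treatment samples; the other two leave no dosing-day sample. In the AG019 cohorts the recommended Friday start puts Day 56 on a Thursday, so there is no such pressure.

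**Blood PK.** The Day 56 blood sample moves with the visit. For a Day 57 or 58 visit it is taken 1 or 2 days after the last dose. The Day 12 sample is on treatment for every repeat dose patient still taking AG019 then.

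**The case against.** The strongest defence is that the protocol gives an explicit rule that sites can follow. It states the window, says where sampling starts, and tabulates every case. Collection times are recorded, so results can be analysed by actual time. The endpoint is descriptive and secondary.

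Most of that stands, and it rules out several stronger readings that a reader might infer:

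- **That late-visit patients have no on-treatment PK sample at all.** This is true of feces only. Blood has Day 12.
- **That every sample number spans 4 days off drug.** Sample 1 does not; its off-drug range is about 0 to 2 days.
- **That the heading flatly contradicts the table.** The heading is better read as the nominal case, which matches the Day 56 row. The heading and the Day 64 endpoint are incomplete for the other four rows.
- **That feces results will be pooled by sample number.** No text says so. The documents give no timing rule for feces in either direction.
- **That Day 57 and Day 58 samples are simply off drug.** A Day 57 sample may follow the Day 56 evening dose by hours. Section 3.4 ties residence to intestinal transit, and Section 5.2.1 requires a 7-day wash-out before re-enrollment. Such a sample may still partly reflect the last dose.

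What the defence does not answer is that re-timing cannot create a dosing-day sample that was never taken, or lengthen a series that stopped at +6 days.

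**Conclusion.** The point holds for feces. Relative to Day 56, samples 2 to 5 each vary by 4 days across the permitted visit days. A Day 54 visit gives three post-treatment samples against four or five for the other visit days. A Day 57 or 58 visit gives no feces sample from a dosing day. For blood PK, the loss at a Day 57 or 58 visit is confined to the end-of-treatment on-drug sample.

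The consequence is limited to a descriptive secondary PK endpoint. The primary endpoint of treatment-emergent adverse events is unaffected. The change is worth making because it is cheap.

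Assumptions:
- Patients dose as scheduled to the evening of Day 56.
- Section 7 lists all feces samples; the Appendix A visit schedule is not in the text available.
- Off-day visits are likely in the combination cohorts if the recommended Monday start is followed and visits are kept to weekdays. The documents do not say how many patients were seen on each day, so that number could be anywhere from none to all of those sampled.

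**What to change.** **Protocol.** Anchor feces sampling to the last dose. Take one sample on or before Day 56, at home if the visit is on Day 57 or 58, then one on each of Days 58, 60, 62 and 64 for every patient. Replace the table with these days, which also brings it into line with the heading. The post-treatment offsets become +2, +4, +6 and +8 for everyone, with one dosing-day sample each.

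**Samples already collected.** Summarise feces and end-of-treatment PK blood by actual days since the last recorded dose, using the recorded collection dates. Report how many patients lack a dosing-day feces sample. State this rule wherever the PK analysis is specified, since the SAP does not cover PK.

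**Cost.** The number of samples stays at five per patient. Home collection and freezer storage are already in the protocol. The added burden is that kits must be issued before the end-of-treatment visit. The preceding visit common to all these patients is Day 28, so kits and instructions could be given out then.
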